### **9.1.7 Unscheduled Visits**

Unscheduled examinations may be conducted at the discretion of the Investigator with all obtained information recorded in the source documents and on the appropriate eCRF. The subject should be scheduled to return for the next scheduled study visit within the acceptable time window.

### **9.1.8 Concomitant Medications and Therapies**

Concomitant medications and concomitant therapies (e.g., physical therapy, pain medication) are recorded at any time from enrollment into the study through the subject's last study visit.

#### **Concomitant Medications**

##### Excluded Concomitant Medications

There are no restrictions on concomitant medications for this study.

##### Recording Concomitant Medications in the eCRF

Only medications related to the study treatment and medications used to treat an adverse event related to the study device and device deficiency will be recorded in

#### CONFIDENTIAL AND PROPRIETARY

This document contains information that is confidential and proprietary to Smith & Nephew PLC and Smith & Nephew, Inc. and is intended for use only by Smith+Nephew and its manufacturer. It shall not be reproduced or copied in whole or in part, nor shall the contents be disclosed by any means without prior written permission from Smith+Nephew, nor shall anyone make any use of it that is contrary to the expressed or implied wishes of Smith+Nephew.

Clinical Protocol	Study Number: CORI.2019.06
A Prospective, Multi-center, Randomized Controlled Study to Evaluate the Safety and Effectiveness of REAL INTELLIGENCE™ CORI™ in unicondylar knee arthroplasty (UKA) Procedure	Version: 4.0-Master, 07 Sep 2022
	Page: 67 of 167

the eCRF. Reference the eCRF Completion Guidelines for how medications are recorded.

## **Concomitant Therapies**

### Therapies Prohibited During the Study

There are no restrictions on concomitant therapies for this study.

### Recording Concomitant Therapies in the eCRF

Only therapies related to the study treatment and therapies used to treat an adverse event related to the study device and device deficiency will be recorded in the eCRF. Reference the eCRF Completion Guidelines for how therapies are recorded.

### **9.1.9 Discontinued Subjects**

Discontinued subjects are those who voluntarily discontinue participation, who are withdrawn for reasons of safety or use of prohibited concomitant medications/therapies, who are lost to follow-up, refer to Section 7.8 for further details. Where possible, the next scheduled study visit should be completed for all subjects who discontinue the study early. Where consent is withdrawn, the date and any reason given for discontinuation should be captured, at a minimum (see Section 7.8.3).

Finally, if appropriate, the Investigator will also advise the subject of subsequent therapy and/or procedures necessary for their medical condition.

### **9.1.10 Subject Pregnancy**

Women of child-bearing potential are not excluded from the study. However, if a woman becomes pregnant during the study, S+N must be contacted immediately

#### CONFIDENTIAL AND PROPRIETARY

This document contains information that is confidential and proprietary to Smith & Nephew PLC and Smith & Nephew, Inc. and is intended for use only by Smith+Nephew and its manufacturer. It shall not be reproduced or copied in whole or in part, nor shall the contents be disclosed by any means without prior written permission from Smith+Nephew, nor shall anyone make any use of it that is contrary to the expressed or implied wishes of Smith+Nephew.

Clinical Protocol	Study Number: CORI.2019.06
A Prospective, Multi-center, Randomized Controlled Study to Evaluate the Safety and Effectiveness of REAL INTELLIGENCE™ CORI™ in unicondylar knee arthroplasty (UKA) Procedure	Version: 4.0-Master, 07 Sep 2022
	Page: 68 of 167

once the investigator is made aware of the pregnancy. All study procedures that are contraindicated during pregnancy and/or lactation (e.g., x-rays) will not be required. A decision will be made regarding the continuation in the study of the pregnant woman. Pregnancy is not an adverse event; however, complications related to the pregnancy may be reportable as determined on a case-by-case basis. Pregnancy-related information will be collected until the end of the pregnancy.

## 9.2 STUDY METHODS AND MEASUREMENTS

[figure not shown]
### 9.2.1 Leg alignment

The leg alignment should be measured from an antero-posterior (A/P) view standing weight bearing full leg ('long leg') x-ray. The following axes shall be identified:

- Mechanical Axis of the femur: Axis from the center of the femoral head to the center of the distal femur.
- Mechanical Axis of the tibia: Axis from the center of the proximal to the center of the distal tibia.

The angular deviation from the neutral position ( $180^\circ$ ) shall be measured as shown as "E" in Figure 9.2-9-1. The angular deviation from the neutral position shall be recorded in the eCRF.

**Figure 9.2-9-1 Leg alignment**

Red: Mechanical Axis of Femur: Axis from the center of the femoral head to the center of the distal femur

Yellow: Mechanical Axis of Tibia: Axis from the center of the proximal to the center of the distal center of the tibia.

Blue: Neutral position axis ( $180^\circ$ ).

E: Deviation angle from the neutral position.

CONFIDENTIAL AND PROPRIETARY

This document contains information that is confidential and proprietary to Smith & Nephew PLC and Smith & Nephew, Inc. and is intended for use only by Smith+Nephew and its manufacturer. It shall not be reproduced or copied in whole or in part, nor shall the contents be disclosed by any means without prior written permission from Smith+Nephew, nor shall anyone make any use of it that is contrary to the expressed or implied wishes of Smith+Nephew.

TMP-CD-05-01 Clinical Protocol - Device - Revision D; SOP-CD-05 Clinical Protocol

Clinical Protocol	Study Number: CORI.2019.06
A Prospective, Multi-center, Randomized Controlled Study to Evaluate the Safety and Effectiveness of REAL INTELLIGENCE™ CORI™ in unicondylar knee arthroplasty (UKA) Procedure	Version: 4.0-Master, 07 Sep 2022
	Page: 70 of 167

### Pre-Operative Leg alignment

The pre-operative leg alignment evaluated from a standing weight bearing long leg standing A/P shall be recorded.

### Target Leg alignment (Surgical Plan)

The operative plan for leg alignment as entered in CORI shall be recorded in the eCRF for each subject. The planned leg alignment serves as the target for post-operative leg alignment. This may not be a neutral position.

### Pre- & Post-Cementation Leg alignment (for CORI UKA only)

The pre-cementation leg alignment shall be recorded with the use of CORI (manual screenshot to be taken) with the trials implant is placed.

Once the final implant has been cemented the post-cementation leg alignment shall be recorded with CORI (manual screenshot to be taken).

### Post-Operative Leg alignment

The leg alignment shall be assessed post-operatively and 6 weeks after surgery on standing weight bearing long leg A/P X-ray and lateral X-ray. Optionally, leg alignment can be assessed optionally at 12 months, in case a standing weight bearing long leg A/P X-ray is taken at 12 months.

Post-operative leg alignment is achieved when the deviation from the subject specific target does not exceed  $\pm 3$  degrees.

All leg alignment measures will be added to the eCRF.

### 9.2.2 Component Alignment

Component alignment will be assessed on long leg standing A/P X-rays and standard non-weight bearing lateral X-rays taken 6 weeks after surgery (or at discharge). The following angles will be evaluated on the X-rays and recorded in the eCRF:

#### A/P View

- **Femoral A/P Angle:** From the A/P radiograph, the femoral flexion angle is to be obtained using standard radiographic tools. Femoral flexion angle is defined as the angle formed between a line across the base of the femoral condyles and a line that is centered along the femoral canal
- **Tibial A/P Angle:** From the A/P radiograph, the tibial angle denotes the angle formed on the medial side of the knee from intersecting lines parallel to the tibial base plate and a line drawn parallel to the tibial canal (Figure 9.2-9-2).
- **Total Valgus Angle:** Is the sum of the femoral flexion angle and the tibial angle.

**Figure 9.2.2-9-2 A/P View**

A: Femoral A/P Angle  
B: Tibial A/P Angle  
A+B: Total Valgus Angle

#### Lateral View

- **Femoral Flexion Angle:** The lateral view femoral flexion angle is obtained from the intersection of a line from the center of the femoral implant to the top of the femur with a

#### CONFIDENTIAL AND PROPRIETARY

[figure not shown]
This document contains information that is confidential and proprietary to Smith & Nephew PLC and Smith & Nephew, Inc. and is intended for use only by Smith+Nephew and its manufacturer. It shall not be reproduced or copied in whole or in part, nor shall the contents be disclosed by any means without prior written permission from Smith+Nephew, nor shall anyone make any use of it that is contrary to the expressed or implied wishes of Smith+Nephew.

Clinical Protocol	Study Number: CORI.2019.06
A Prospective, Multi-center, Randomized Controlled Study to Evaluate the Safety and Effectiveness of REAL INTELLIGENCE™ CORI™ in unicondylar knee arthroplasty (UKA) Procedure	Version: 4.0-Master, 07 Sep 2022
	Page: 72 of 167

line through the femoral canal. The angle is measured on the proximal side of the intersection

- **Tibial Lateral Angle:** The lateral view tibial angle is the angle obtained from the intersection of a line drawn parallel to the bottom of the tibial base insert and a line through the center of the tibial base and the tibial canal.

**Figure 9.2.2-9-3**  
**Lateral View**

X: Femoral Flexion Angle  
Y: Tibial Lateral Angle

### 9.2.3 Standard Radiographic Evaluation

Standard radiographic evaluation on antero-posterior (A/P) and lateral views shall be performed 12 months after surgery in order to identify any radiographic observations such as radiolucent lines around the implant components. The presence of radiolucent lines, osteolysis & implant migration shall be recorded in the eCRF.

### 9.2.4 2011 Knee Society Score (2011 KSS)

The 2011 Knee Society Score will be collected at the pre-operative visit and 6 weeks, 6- and 12-months after surgery.

The 2011 KSS is a validated tool that combines an objective physician-derived component with a subjective subject-derived component [45, 46]. The 2011 KSS consists of 34 questions and provides sub-scores across 4 dimensions as shown in Table 9.2.4-9-2.

**Table 9.2.4-9-2 2011 Knee Society Score**

#	Sub-Score	# Questions	Completion by
1	Objective Knee Score	4	Surgeon

#### CONFIDENTIAL AND PROPRIETARY

This document contains information that is confidential and proprietary to Smith & Nephew PLC and Smith & Nephew, Inc. and is intended for use only by Smith+Nephew and its manufacturer. It shall not be reproduced or copied in whole or in part, nor shall the contents be disclosed by any means without prior written permission from Smith+Nephew, nor shall anyone make any use of it that is contrary to the expressed or implied wishes of Smith+Nephew.  
TMP-CD-05-01 Clinical Protocol - Device - Revision D; SOP-CD-05 Clinical Protocol

Clinical Protocol		Study Number: CORI.2019.06
A Prospective, Multi-center, Randomized Controlled Study to Evaluate the Safety and Effectiveness of REAL INTELLIGENCE™ CORI™ in unicondylar knee arthroplasty (UKA) Procedure		Version: 4.0-Master, 07 Sep 2022
		Page: 73 of 167

2	Symptoms	3	Subject
2	Subject Satisfaction Score	5	Subject
3	Subject Expectation	3	Subject
4	Functional Knee Score	19	Subject

The Objective Knee Score is rated by the clinician and assesses a range of clinical outcomes: UKA alignment, stability, ROM and symptoms. The Subject Satisfaction Score assesses the satisfaction with 5 daily activities (sitting, lying in bed, getting out of bed, light household duties, and leisure activities). The Subject Expectation Score evaluates the subject's expectations prior to surgery. The post-operative questions differ from the pre-operative questions and ask if the subject's pre-operative expectations have been met. As the pre- and post-operative scores are based on different questions, they cannot be directly compared. The Functional Knee Score is derived from assessments of walking and standing, standard activities, advanced activities, and discretionary activities.

A paper questionnaire will be provided by the Sponsor to be completed by the subject. Responses for the 2011 KSS will then be recorded in the eCRF.

### **9.2.5 Oxford Knee Score (OKS)**

The OKS will be collected at the pre-operative visit and 6 weeks, 6- and 12-months after surgery.

The OKS is a Patient Reported Outcome questionnaire that was developed to specifically assess the patient's perspective of outcome following Total Knee Arthroplasty. The OKS is a patient self-completion PRO containing 12 equally weighted questions on activities of daily living. The OKS has been developed and validated specifically to assess perceived function and pain answered on a Likert scale after TKA [47, 48]. Responses to each question ranges from 0-4 with a range of a

#### CONFIDENTIAL AND PROPRIETARY

This document contains information that is confidential and proprietary to Smith & Nephew PLC and Smith & Nephew, Inc. and is intended for use only by Smith+Nephew and its manufacturer. It shall not be reproduced or copied in whole or in part, nor shall the contents be disclosed by any means without prior written permission from Smith+Nephew, nor shall anyone make any use of it that is contrary to the expressed or implied wishes of Smith+Nephew.

Clinical Protocol	Study Number: CORI.2019.06
A Prospective, Multi-center, Randomized Controlled Study to Evaluate the Safety and Effectiveness of REAL INTELLIGENCE™ CORI™ in unicondylar knee arthroplasty (UKA) Procedure	Version: 4.0-Master, 07 Sep 2022
	Page: 74 of 167

possible overall score from 0-48. A score of 0 is the worst possible outcome while a score of 48 is the best possible outcome. The benefit to this questionnaire is that it is short, practical, reliable, valid and sensitive to clinically important changes over time.

A paper questionnaire will be provided by the Sponsor to be completed by the subject. Responses for the OKS will then be recorded in the eCRF.

#### **9.2.6 Forgotten Joint Score (FJS-12)**

The FJS-12 will be collected at 6 weeks, 6- and 12-months after surgery. A paper questionnaire will be provided by the Sponsor to be completed by the subject.

The FJS-12 comprises measures for the assessment of joint-specific patient reported outcomes. This questionnaire focuses on the study subject's awareness of the partially or fully replaced knee joint in everyday life. Joint awareness can be simply defined as any unintended perception of a joint [49]. Subjects are asked to rate their awareness of their knee arthroplasty in 12 questions with a five point Likert response format: "Never", "almost never", "seldom", "sometimes" and "mostly". The item scores are summed and linearly transformed in a 0 to 100 scale with a high value reflecting the ability of the subject to forget about the replaced knee joint during the activities of daily living.

A paper questionnaire will be provided by the Sponsor to be completed by the subject. Responses for the FJS-12 will then be recorded in the eCRF.

#### **9.2.7 CORI System Time & Cutting Time**

CORI System Time and the Cutting Time of the robotic drill shall be collected post-operatively.

CORI Case Report, including case logs, will be extracted from CORI via USB and time data will be extracted for CORI System Time and the Cutting Time

#### CONFIDENTIAL AND PROPRIETARY

This document contains information that is confidential and proprietary to Smith & Nephew PLC and Smith & Nephew, Inc. and is intended for use only by Smith+Nephew and its manufacturer. It shall not be reproduced or copied in whole or in part, nor shall the contents be disclosed by any means without prior written permission from Smith+Nephew, nor shall anyone make any use of it that is contrary to the expressed or implied wishes of Smith+Nephew.

Clinical Protocol	Study Number: CORI.2019.06
A Prospective, Multi-center, Randomized Controlled Study to Evaluate the Safety and Effectiveness of REAL INTELLIGENCE™ CORI™ in unicondylar knee arthroplasty (UKA) Procedure	Version: 4.0-Master, 07 Sep 2022
	Page: 75 of 167

In the case logs, the following time stamps will be recorded in the log file of the CORI Case Report:

1. State-Machine transition : [ Adjust Camera ] --> [ Checkpoint Definition ]
2. State-Machine transition : [ Checkpoint Verification ] --> [ Remove Bone ]
3. State-Machine transition : [ Remove Bone ] --> [ Baseline Stress ROM Collection ]

#### CORI System Time

CORI System starts with the checkpoint definition until the bone is removed. This is calculated by the time difference between #3 and #1.

#### Cutting Time

The Cutting Time of the robotic drill is the time from the start until the end of bone removal and is calculated by the time difference between #3 and #2.

The CORI System time and the cutting time of the robotic drill will not be recorded in the eCRF as they will be extracted directly from the CORI Case Report.

### **9.3 HEALTH ECONOMICS/QUALITY OF LIFE**

#### **9.3.1 EQ-5D-5L**

The EQ-5D-5L questionnaire will be collected at the pre-operative visit as well as 6 weeks, 6- and 12-months after surgery. A paper questionnaire will be provided by the Sponsor to be completed by the subject.

The EQ-5D-5L essentially consists of 2 pages: the EQ-5D descriptive system and the EQ visual analogue scale (EQ VAS).

#### CONFIDENTIAL AND PROPRIETARY

This document contains information that is confidential and proprietary to Smith & Nephew PLC and Smith & Nephew, Inc. and is intended for use only by Smith+Nephew and its manufacturer. It shall not be reproduced or copied in whole or in part, nor shall the contents be disclosed by any means without prior written permission from Smith+Nephew, nor shall anyone make any use of it that is contrary to the expressed or implied wishes of Smith+Nephew.  
TMP-CD-05-01 Clinical Protocol - Device - Revision D; SOP-CD-05 Clinical Protocol

Clinical Protocol	Study Number: CORI.2019.06
A Prospective, Multi-center, Randomized Controlled Study to Evaluate the Safety and Effectiveness of REAL INTELLIGENCE™ CORI™ in unicondylar knee arthroplasty (UKA) Procedure	Version: 4.0-Master, 07 Sep 2022
	Page: 76 of 167

The descriptive system is used to describe the subject's health state and consists of five dimensions: mobility, self-care, usual activities, pain/discomfort, and anxiety/depression. Each dimension has 5 levels to choose the most appropriate answer: no problems, slight problems, moderate problems, severe problems, and extreme problems. The subject is asked to indicate his/her health state by marking the most appropriate statement in each of the five areas [50].

The EQ VAS records the subject's self-rated health on a vertical visual analogue scale. The endpoints on the scale are labelled "The best health you can imagine" and "The worst health you can imagine". The VAS can be used as a quantitative measure of health outcome as judged by the individual respondents.

A paper questionnaire will be provided by the Sponsor to be completed by the subject. Responses for the EQ-5D-5L Score will then be recorded in the eCRF.

## 10 STATISTICAL DESIGN

A Statistical Analysis Plan (SAP) will be written and finalized prior to database lock.

The following is a brief description of the analyses to be described in this plan.

### 10.1 GENERAL

S+N's Global Biostatistics group will conduct the statistical analysis for this study. Unless otherwise stated, all significance tests and hypothesis testing will be two-sided, performed at the 5% significance level. Resulting p-values will be quoted and 95% two-sided confidence intervals will be generated where appropriate. Where data summaries are specified, categorical and ordinal variables will be summarized with frequencies and percentages. Continuous variables will be summarized with the following summary statistics: the number of observations, mean, median, standard deviation, minimum and maximum values.

All statistical comparisons of data will describe the test statistic used as well as its distributional assumptions. For continuous variables, in an event of marked deviation from normality assumption, a commensurate non-parametric test would be used as an alternative thereby eliminating the possibility of violation of normality assumptions. All analyses will be performed using SAS version 9.3 (or a later version).

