### 2011 Knee Society Score (KSS)

The 2011 KSS objective, function and satisfaction scores will be summarized at the pre-operative and postoperative visits using continuous summary characteristics. For each of these 3 KSS scores, independent repeated measures Analysis of Covariance (ANCOVA) models (to account for the correlation between subjects with bilateral knees) will be used to model the change from preoperative to postoperative KSS scores as the dependent variable. As a minimum, each model will contain a group (pre-operative and postoperative) and the investigational site as a fixed term with a repeated specification for the knee. Pre-operative prognostic and demographic variables not only restricted to age, BMI and sex, but that can also be ascertained to have an impact on the KSS scores will be introduced as covariates in the final model. These covariates will be added to the model using a stepwise approach and a covariate is retained in the final model if and only if its associated p-value  $\leq 0.1$ . Model based means (adjusted means or Least Square Means, LSMeans) and corresponding standard errors associated with each change from preoperative to postoperative KSS score will be presented by group. Model based

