#### CONFIDENTIAL AND PROPRIETARY

This document contains information that is confidential and proprietary to Smith & Nephew PLC and Smith & Nephew, Inc. and is intended for use only by Smith+Nephew and its manufacturer. It shall not be reproduced or copied in whole or in part, nor shall the contents be disclosed by any means without prior written permission from Smith+Nephew, nor shall anyone make any use of it that is contrary to the expressed or implied wishes of Smith+Nephew.  
 TMP-CD-05-01 Clinical Protocol - Device - Revision D; SOP-CD-05 Clinical Protocol

Clinical Protocol	Study Number: CORI.2019.06
A Prospective, Multi-center, Randomized Controlled Study to Evaluate the Safety and Effectiveness of REAL INTELLIGENCE™ CORI™ in unicondylar knee arthroplasty (UKA) Procedure	Version: 4.0-Master, 07 Sep 2022
	Page: 83 of 167

preoperative to postoperative visits will also be summarized. In the case of bilateral knees, repeated measures ANCOVA models will account for correlation between subjects with bilateral knees each for the index score and VAS analogous to that specified for the 2011 KSS will be used.

The 2011 KSS, transformed FJS-12 and EQ-5D-5L scores will additionally be summarized by group (i.e. the CORI Navigational and Conventional manual instrumentation groups) and visit using descriptive statistics for continuous variables.

The Multiple Imputation (MI) missing value imputation method will be used as the imputation method for missing 2011 KSS, FJS-12, OKS, and EQ-5D-5L endpoints. Details of the MI method will be included in the SAP.

All secondary endpoints will be summarized using the FAS analysis population.

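### Section 10.1 lets an unnamed non-parametric test replace the planned ANCOVA on an undefined normality judgement, so the analysis of the secondary scores is chosen after the outcome data are seen

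*Protocol*

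**What the plan says.** Protocol Section 10.1 sets general rules: "all significance tests and hypothesis testing will be two-sided, performed at the 5% significance level". For continuous variables it adds that "in an event of marked deviation from normality assumption, a commensurate non-parametric test would be used as an alternative", and presents this as a way of removing any risk that normality is violated. No diagnostic, threshold or replacement test is given.

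Section 10.4.2 plans a repeated measures ANCOVA for the three KSS scores, and analogous models for OKS, FJS-12 and EQ-5D-5L. For KSS it will "model the change from preoperative to postoperative KSS scores as the dependent variable". The guaranteed terms are these: "As a minimum, each model will contain a group (pre-operative and postoperative) and the investigational site as a fixed term". Further covariates are optional. They are drawn from "Pre-operative prognostic and demographic variables not only restricted to age, BMI and sex", entered stepwise, and "a covariate is retained in the final model if and only if its associated p-value" is at most 0.1. The promised output is "Model based means (adjusted means or Least Square Means, LSMeans) and corresponding standard errors associated with each change from preoperative to postoperative KSS score", by group, plus model-based differences between CORI and conventional instrumentation with 95% CIs. For missing data, "The Multiple Imputation (MI) missing value imputation method will be used as the imputation method for missing 2011 KSS, FJS-12, OKS, and EQ-5D-5L endpoints", with details left to the SAP.

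The SAP does not fill the gap. Sections 2, 7.1 and 7.15 record that the study stopped with four subjects and that listings replace all statistical analysis. Sections 7.3 and 7.11 are marked not applicable.

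**The concern.** A switch of method with no criterion is a choice made after the outcome data are visible. The trial is non-blinded (Section 8.2.2), the sponsor's own biostatistics group runs the analysis (Section 10.1), and Section 8.5.4 promises that the details of all analyses will be pre-specified. The scores could end up with different methods, and so with different quantities being estimated.

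The switch is plausible in practice. OKS runs from 0 to 48, FJS-12 from 0 to 100 and KSS satisfaction from 0 to 40, so ceilings after surgery can be expected. KSS objective is an exception, since the SAP allows it to exceed 100.

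The rationale is also weak. A linear model's assumption concerns residuals, not raw scores, and with about 63 to 70 per arm its group comparison tolerates moderate skew. The switch may therefore give up the planned estimates for little protection.

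**Working it through.** **1. What a standard two-sample rank test would keep or lose**

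| Planned in 10.4.2 | After a Mann-Whitney test |
|---|---|
| Site as a fixed term (site is the randomisation block, Section 8.2.1) | Lost |
| Any covariates retained stepwise | Lost |
| LSMeans and standard errors by group | Lost |
| Model-based difference with 95% CI | Lost |
| Pre-operative value, through the change score | Kept, if the test is on change |
| Pre-operative score as a covariate | Not guaranteed in the plan; FJS-12 has no pre-operative value (Section 9.2.6) |
| Multiple imputation of missing scores | Kept, but no pooling method: the usual rules combine an estimate and its variance, not a rank-test p-value |

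This part needs no simulation. It does assume an ordinary rank test. It also reads the group term as treatment group: the protocol's parenthesis describes it as pre-operative and postoperative, but the differences reported are between the two arms.

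**2. The plan's own figure**

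The only power statement in the documents is Section 11, for the binary primary endpoint. With p1 = 0.921, p0 = 0.734, mean 0.8275, two-sided 5% and 80% power:

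n = [1.960 × √(2 × 0.8275 × 0.1725) + 0.8416 × √(0.921 × 0.079 + 0.734 × 0.266)]² / 0.187²
= (1.0473 + 0.4357)² / 0.03497 ≈ 62.9, so 63 per group (power 80.1%).

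63 / 0.90 = 70. Both figures reproduce, and nothing in this point changes them.

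**3. Size on a bounded score (illustration)**

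The documents give no SD, correlation or effect size for the scores, so every distributional input here is assumed. There are 63 per arm and 8 sites, with allocation balanced within site. The score is rounded and limited to 0–48:

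- pre-operative = 22 + 8b;
- postoperative = 41 + site effect (SD 2) + 9 × [ρb + √(1−ρ²)e] + 5 × group, with b and e standard normal.

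One postoperative visit, no missing data, 2,000 trials per setting. Power at two-sided 5%:

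| Analysis | ρ = 0.3 | ρ = 0.5 | ρ = 0.7 |
|---|---|---|---|
| A. Change on group, site, pre-operative score | 0.841 | 0.893 | 0.961 |
| B. Change on group, site (guaranteed terms) | 0.563 | 0.699 | 0.842 |
| C. Rank test on change | 0.537 | 0.664 | 0.818 |
| D. Rank test on postoperative score | 0.817 | 0.816 | 0.803 |

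Differences, from the unrounded results:

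- B − C: 0.5630 − 0.5365 = 0.027; 0.6985 − 0.6635 = 0.035; 0.8420 − 0.8175 = 0.025. About 2 to 4 points.
- A − C: 0.8405 − 0.5365 = 0.304; 0.8930 − 0.6635 = 0.230; 0.9605 − 0.8175 = 0.143. About 14 to 30 points.

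**4. Is the switch needed for validity?**

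With no true difference, type I error was 6.0%, 5.4% and 5.1% for A, and 5.0%, 5.1% and 6.1% for B. Simulation error at 5% is √(0.05 × 0.95 / 2000) ≈ 0.5 points, so both are close to nominal despite the ceiling. A 5% Shapiro-Wilk test on the residuals of A rejected in 88%, 64% and 27% of the same null trials. That is only a stand-in for the protocol's undefined trigger. It shows that a formal normality test can fire often when the model is performing acceptably.

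**The case against.** The case against is strong on several points, and most of it stands.

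- **The trigger is narrower than any non-normality.** The text requires a marked deviation, and a residual-based reading is open. A reader might infer that the rule would almost always fire, because a 5% normality test on the raw scores nearly always rejects. The protocol specifies no such test, and the variable modelled is change.
- **The word *commensurate* leaves room for a rank-based method that keeps covariates.** The losses listed above therefore depend on the replacement chosen. But the protocol does not choose it, so the uncertainty remains.
- **Baseline-score adjustment is not promised.** A reader might infer a power loss of about 12 points. Under another set of assumed inputs (0–48 score, mean 38, SD about 8, correlation 0.5, difference 4, 63 per arm), ANCOVA with arm, pre-operative score and site gave 84.5% against 72.0% for a rank test on change. That comparator includes a covariate that Section 10.4.2 does not guarantee, so the gap cannot be charged to Section 10.1. Row D even beats row B at two of the three correlations.
- **Multiple imputation is not withdrawn.** A reader might infer that it is. Section 10.4.2 specifies it without reference to the test; only the pooling of rank tests is missing.
- **Keeping the 10.4.2 models does not remove all data dependence,** because covariates are still selected stepwise. That is correct, and is why the fix also names the pre-operative score as fixed.
- **The stakes are low.** Only secondary scores are affected, Section 10 describes itself as brief, and no model is run under the SAP.

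None of this supplies a criterion or a named test, or exempts the 10.4.2 models from the rule.

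**Conclusion.** The point holds in limited form. Section 10.1 contains a data-dependent rule with no criterion and no named replacement, and it reaches the ANCOVA models for KSS, OKS, FJS-12 and EQ-5D-5L. If an ordinary rank test were substituted, the site term, any retained covariates, the LSMeans and the adjusted difference with its 95% CI would go, and pooling over imputations would be undefined. That conclusion rests on the text.

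The power cost rests on assumed inputs: about 2 to 4 points against the guaranteed model on change. The larger loss applies only if the pre-operative score is in the model. The simulation did not evaluate the error rate of the two-stage procedure itself.

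The primary endpoint and sample size are unaffected. With four subjects and listings only, no reported result changes. The text still merits correction, because Section 8.1 says the data may be combined with the parallel CORI cohort study and refers to Section 10 for how.

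**What to change.** Replace the sentence in Section 10.1 with a statement to this effect:

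- The Section 10.4.2 models are the analysis of the secondary scores whatever the distribution of the variable. Site is kept, and the pre-operative score is a fixed covariate wherever it is collected (so not for FJS-12).
- Residuals are inspected. If they are clearly non-normal or heteroscedastic, the same model is reported with robust (sandwich) or bootstrap standard errors.
- Any rank-based analysis is pre-specified and serves as a sensitivity analysis only.

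The estimated difference and its CI then mean the same thing for a given score whatever the data look like, and the usual pooling over imputations can apply. The cost is a short change of protocol text and a little extra programming; the sample size does not change. Stepwise selection of the remaining covariates is a separate matter that this change does not settle.
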